### Abstract

Chronic pain (CP) is a substantial healthcare challenge with considerable economic costs. Recently, the term of Nociplastic Pain (NP) has been advanced as a third descriptor of mechanisms related to CP. NP describes conditions that arise from altered nociception despite no clear evidence of actual or threatened tissue damage. It is a new way of describing somatoform painful conditions, originating from altered central-nervous pathways (e.g., central sensitization) and with the important involvement of clinical psychological factors. Among nociplastic chronic syndromes have been included fibromyalgia (FM), chronic migraine (CM) and vulvodynia (VU). These chronic pain disorders have been usually studied separately, although the high comorbidity rates. Many studies evidenced the role of psychosocial variables in the onset and maintenance of the burden related to these conditions. Among them, personality traits, defense mechanisms, central sensitization, and childhood traumatic experiences may play a pivotal role in the onset of the NP. The first aim of this study is to highlight possible psychosocial clusters of variables that are specific for each condition (FM, CM, and VU). A second aim, to improve the tailored psychological treatment devoted to these conditions, is to explore the association between FM, CM, and VU with depression, anxiety, somatization, quality of life, alexithymia, social support, sexual satisfaction, and functioning. This will make it possible to identify specifically for each condition the areas of greatest interest that can be investigated and treated in clinical intervention. To identify specific descriptors, NP conditions will be compared with a control group of subjects reporting other types of CP (e.g., knee arthrosis, rheumatoid arthritis). The study involves the collection of data from a self-administered questionnaire in several Italian centers specializing in the above-mentioned clinical conditions under the guidance of the research team of the Department of Dynamic and Clinical Psychology and Health Studies, PI [name].

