syndromes have been included chronic migraine, fibromyalgia, and vulvodynia (Bergeron et al., 2020; Fitzcharles et al., 2021). NP is usually accompanied by other central nervous system-associated symptoms with a close link with clinical psychological factors: general symptoms (e.g., fatigue and cognitive problems), temperamental characteristics (e.g., hypersensitivity to environmental stimuli) and psychological symptoms (e.g., anxiety/depression) (Fitzcharles et al., 2021). Many emotional states, such as depression and anxiety, and emotional processes, such as emotional awareness and regulation, may influence the presence and severity of NP (Aaron et al., 2020; Lumley et al., 2021), opening to the importance of a psychological assessment for diagnosis and psychological interventions. The concept of NP opens a new framework for understanding the co-occurrence of different chronic disorders and the role of related psychological factors. Comorbid chronic disorders may be the expression of shared pathophysiological mechanisms, with etiological and psychological features differentiating them by “pure” forms of the same disease. The comorbid association of migraine, fibromyalgia, and vulvodynia, and the well-known link with clinical psychological factors (e.g., early traumatic events, anxiety and depression, alexithymia, dissociation, etc.) is quite established (Bergeron et al., 2020; Fitzcharles et al., 2021). However, these chronic pain disorders have been usually studied as separate diseases. On the one hand, this research project wants to observe the common basis of these chronic pain disorders, which can be traced back to central sensitization mechanisms, the influence of early adverse events, and other psychological factors, and on the other hand it wants to observe the psychosocial peculiarities of each assessed condition (fibromyalgia, migraine, and vulvodynia) for tailored treatment purposes.

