### Aims

The first aim of this study is to highlight possible psychosocial clusters of variables that are specific to the onset and maintenance for each condition (FM, CM, and VU). Specifically, the observation of possible clusters will be made based on variables such as personality traits, defense mechanisms, central sensitization, and childhood traumatic experiences. The hypothesis is that specific psychological factors (clusters of high number of early traumatic events, high levels of central sensitization, and specific traits and defense mechanisms) characterize FM, CM, and VU groups compared to controls reporting other types of CP (e.g., knee arthrosis, rheumatoid arthritis).

A second aim, to give directions for tailored psychological treatments devoted to these conditions, is to explore the association between FM, CM, and VU with depression, anxiety, somatization, quality of life, alexithymia, social support, sexual satisfaction, and functioning. In line with our hypothesis that each of

these conditions has specific areas of psychological sensitivity, this will make it possible to identify specifically for each condition the areas of greatest interest that can be investigated and treated in clinical intervention.

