#### STATYSTICAL PLANNED ANALYSES

The required sample size was estimated a priori for the ANOVA procedure that tested the cluster model sensitivity having 4 groups (migraine, fibromyalgia, vulvodynia, and controls). Using the G\*power program,  $p = 0.05$ , statistical power of 85%, and effect size of 0.35, the calculation yielded a total sample size of  $n = 108$  participants per group (432 as total) The four centers involved in the recruitment of the participants will be the Università di Milano IRCCS Sant'Ambrogio Galeazzi under the head of [name] and Dott. [name], the IRCCS Mondino di Pavia under the head of [name] and [name], The Policlinico San Matteo of Pavia under the head of [name] and Dott. [name], and the Policlinico Umberto I of Sapienza University of Rome under the head of Dott. [name].

ANOVAs and  $\chi^2$  analyses will be carried out to compare groups on sociodemographic characteristics for descriptive reasons and to select possible covariates based on selection bias.

A group of cluster analyses will be performed to classify the samples based on personality traits, defense mechanisms, central sensitization, and childhood traumatic experiences (twenty-two variables corresponding to total scores and thematic subscales of the related measures), aiming to identify different clinical phenotypes within the study samples. A statistical procedure of Two-Step Cluster Analysis will be preferred due to its ability to ensure that one variable does not dominate the cluster solution. Furthermore, it enables the user to identify the importance of each item in the cluster solution. The model fit will be assessed by Schwarz's Bayesian Information Criterion and evaluated by the average silhouette coefficient, an internal validity index representing cluster cohesion and separation quality, ranging between 0 and 1; the closer to 1, the better the model.

Crosstab analyses will be performed to test the association and their strength, and MANOVAs to detect differences in the classification variables based on cluster groups, and Pearson's correlation to explore associations among clusters and other psychological domains. The statistical analyses will be performed using IBM SPSS v. 27.0 and AMOS v.22 (SPSS Inc., Chicago, IL, USA).

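### Aim 1 asks for clusters specific to each of FM, CM and VU, but the only stated comparator is the control group, and no contrast among the three conditions or rule for specificity is planned

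*Combined protocol and SAP*

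**What the plan says.** The Abstract gives the first aim as to "highlight possible psychosocial clusters of variables that are specific for each condition (FM, CM, and VU"). The Aims section repeats it as "psychosocial clusters of variables that are specific to the onset and maintenance for each condition (FM, CM, and VU").

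Two statements say what these conditions are compared with. The Abstract: "To identify specific descriptors, NP conditions will be compared with a control group of subjects reporting other types of CP". The hypothesis attached to the first aim says that certain factors "characterize FM, CM, and VU groups compared to controls reporting other types of CP". It lists those factors once for all three conditions: "clusters of high number of early traumatic events, high levels of central sensitization, and specific traits and defense mechanisms".

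The Rational section holds two objectives side by side. One is shared: "this research project wants to observe the common basis of these chronic pain disorders". The other is individual: "it wants to observe the psychosocial peculiarities of each assessed condition (fibromyalgia, migraine, and vulvodynia) for tailored treatment purposes".

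The statistical section bases its sample size on a four-group ANOVA and then plans a Two-Step Cluster Analysis. On linking clusters to diagnoses it says only "Crosstab analyses will be performed to test the association and their strength". The crossed variables are not named. The MANOVAs take cluster membership, not diagnosis, as the factor. No comparison of FM with CM, FM with VU or CM with VU appears, and no criterion for calling a cluster specific to a condition.

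**The concern.** The two objectives in the Rational section predict opposite results among FM, CM and VU: similarity if there is a common basis, difference if each condition has its own profile. A comparison with controls cannot tell these apart, because a profile found equally in all three conditions differs from controls just as one peculiar to a single condition does.

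The protocol's own reasoning makes the shared result plausible. The Rational section traces the common basis to central sensitization and early adverse events, and the same two features lead the hypothesis under the specificity aim. If all three groups fell equally into a high-trauma, high-sensitization cluster, the hypothesis would be confirmed and the first aim would have no support. The proposed use of the results, treatment tailored to each condition, rests on the specific reading and not the shared one.

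**Working it through.** **Plan figures.** The plan gives no power or error figure for this question. From it I take 108 per group and a 0.05 level. The 108 itself does not reproduce as a per-group figure: a four-group ANOVA with effect size 0.35 (read as Cohen's f) and 85% power needs 108 in total (27 per group, power 0.863). That is a separate matter; 108 per group is used here as stated.

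**Assumptions, not in the documents.** Two clusters; the same share p of FM, CM and VU in one of them; 40% of controls in it. By construction nothing is specific to any one condition.

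**Four-group crosstab (4×2).** λ = n·Σ(pᵢ − p̄)² / [p̄(1 − p̄)], with 3 df and critical value 7.815.

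- p = 0.60: p̄ = (3×0.60 + 0.40)/4 = 0.55; Σ = 3×0.05² + 0.15² = 0.030; λ = 108×0.030/0.2475 = 13.1; power 0.873.
- p = 0.55: p̄ = 0.5125; Σ = 3×0.0375² + 0.1125² = 0.016875; λ = 108×0.016875/0.24984 = 7.29; power 0.609.
- p = 0.65: p̄ = 0.5875; Σ = 3×0.0625² + 0.1875² = 0.046875; λ = 108×0.046875/0.24234 = 20.9; power 0.980.

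**Crosstab restricted to FM, CM and VU (3×2).** The three shares are equal, so λ = 0 and the rejection rate is the 5% level. In 20,000 simulated studies at 60/60/60/40 the four-group test rejected in 87.7% and the restricted test in 5.1%. In 82.6% the first was significant and the second was not.

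**Same question on a continuous score.** With one 0.5 SD shift shared by FM, CM and VU and 108 per group (20,000 simulations), all three control comparisons were significant in 89.6%, the four-group test rejected in 97.6%, and the test among the three conditions rejected in 4.9%.

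**Would the restricted crosstab alone be enough?** Take FM 60%, CM 40%, VU 40% and controls 60%. Among the three conditions p̄ = 0.4667; Σ = 0.1333² + 2×0.0667² = 0.02667; λ = 108×0.02667/0.2489 = 11.6 on 2 df (critical value 5.991); power about 0.87. The cluster would pass as specific to FM although FM and controls have identical membership. Specificity therefore needs both comparisons.

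**The case against.** The strongest reply is that the plan is under-specified rather than built on controls alone. The common basis is an objective in its own right, so a shared profile has a natural place in the report. The section on psychological factors gives the knowledge gap as characterizing or differentiating between the nociplastic conditions, and the second aim assumes that each has its own sensitivities. The statistical section keeps four separate groups, speaks of crosstabs in the plural and excludes no contrast. Its most natural reading is cluster by four-level diagnosis, and such a table would show a 60/60/60/40 pattern for what it is. In addition, the traits and defenses in the hypothesis could be meant to differ by condition, and the descriptors in the Abstract could be descriptors of nociplastic pain as a whole, for which other-pain controls are the right comparator.

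Much of this stands. A reader might infer that a shared profile would be reported as condition-specific, or that the three conditions are pooled against controls. The documents support neither. What remains is that the wish to differentiate is stated but no analysis is assigned to it. Inspecting cell percentages without a test or a rule is not a planned inference, and the hypothesis for the first aim names only controls as comparator.

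**Conclusion.** The point holds as a mismatch between the aim and its stated comparator. A shared profile would satisfy the hypothesis without supporting the first aim, and nothing in the statistical section separates the two, so a common nociplastic profile could be labelled condition-specific.

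The 87% (61% to 98% for shares of 55% to 65%) should not be read as an error rate. It is the power to detect a true difference from controls under assumed inputs: two clusters, 40% of controls in one, and 108 per group. The plan leaves the number of clusters to the data. The figure shows only that a significant four-group result is no evidence of specificity; how often it would be mislabelled is not estimated.

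This should be fixed, but it is not critical: the aim is exploratory, to highlight possible clusters, and neither recruitment nor data collection is affected.

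**What to change.** 1. In the statistical section, state that the crosstab is cluster membership by four-level diagnosis (FM, CM, VU, controls).
2. Split the hypothesis under Aims into (a) shared: FM, CM and VU differ from controls; and (b) specific: FM, CM and VU differ from one another. Test (b) with the same crosstab restricted to the three conditions and, if positive, pairwise contrasts with multiplicity control.
3. Call a cluster specific to a condition only when that condition differs both from the other two and from controls. Otherwise report a common nociplastic profile, or no specificity, as the data show.
4. Amend the Abstract sentence on specific descriptors to match.

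The cost is wording plus one more analysis on data already to be collected. The drawback is that condition-specific claims become harder to make. For a 60% against 40% contrast with 108 per group at Bonferroni level 0.05/3 = 0.0167 (critical z 2.394), z = (0.20 − 2.394×√(2×0.25/108)) / √(2×0.24/108) = (0.20 − 0.163)/0.0667 = 0.56, so power is about 71%. For a mean difference of 0.5 SD at the same level it is about 90%. The rule should be set before the clusters are seen.

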### Rational

Chronic pain (CP), defined as pain lasting more than 3 months, is a substantial healthcare challenge. Prevalence rates of CP are between 11% and 40% (Dahlhamer et al., 2018). A systematic review reported a pooled CP prevalence rate of 43.5%, with the rate of moderate-to-severe disabling pain ranging from 10% to 14% (Fayaz et al., 2016). CP prevalence increases with age, is greater among females, and among people with lower socioeconomic status (Tsang et al., 2008; Pergolizzi et al., 2013). CP affects relationships and self-esteem, and is associated with higher divorce and suicide rates, and an increased risk of substance abuse (Tang et al., 2016; Fitzcharles et al., 2021), psychopathology (Katz et al., 2015) and risk of medication overuse (Westergaard et al., 2015). The causes of CP are still poorly understood. Recently, the International Association for the Study of Pain (IASP, 2017) has proposed that three subtypes of CP may be differentiated based on unique causal mechanisms: nociceptive, neuropathic, and nociplastic.

Nociplastic Pain (NP) is a new descriptor of CP and includes conditions that arise from altered nociception despite no clear evidence of actual or threatened tissue damage. NP should be viewed as an overarching terminology that can be applied to a diverse range of clinical conditions that share common neurophysiological mechanisms, involving various organ systems (Galli, 2023). Among nociplastic chronic

syndromes have been included chronic migraine, fibromyalgia, and vulvodynia (Bergeron et al., 2020; Fitzcharles et al., 2021). NP is usually accompanied by other central nervous system-associated symptoms with a close link with clinical psychological factors: general symptoms (e.g., fatigue and cognitive problems), temperamental characteristics (e.g., hypersensitivity to environmental stimuli) and psychological symptoms (e.g., anxiety/depression) (Fitzcharles et al., 2021). Many emotional states, such as depression and anxiety, and emotional processes, such as emotional awareness and regulation, may influence the presence and severity of NP (Aaron et al., 2020; Lumley et al., 2021), opening to the importance of a psychological assessment for diagnosis and psychological interventions. The concept of NP opens a new framework for understanding the co-occurrence of different chronic disorders and the role of related psychological factors. Comorbid chronic disorders may be the expression of shared pathophysiological mechanisms, with etiological and psychological features differentiating them by “pure” forms of the same disease. The comorbid association of migraine, fibromyalgia, and vulvodynia, and the well-known link with clinical psychological factors (e.g., early traumatic events, anxiety and depression, alexithymia, dissociation, etc.) is quite established (Bergeron et al., 2020; Fitzcharles et al., 2021). However, these chronic pain disorders have been usually studied as separate diseases. On the one hand, this research project wants to observe the common basis of these chronic pain disorders, which can be traced back to central sensitization mechanisms, the influence of early adverse events, and other psychological factors, and on the other hand it wants to observe the psychosocial peculiarities of each assessed condition (fibromyalgia, migraine, and vulvodynia) for tailored treatment purposes.

#### CHRONIC MIGRAINE (CM)

Migraine affects ~15% of the general population globally and is typically characterized by recurring, often highly disabling attacks of severe headache, nausea, vomiting, super- sensitivity to light and sound, and other variable physical, mental, and psychological signs and symptoms, lasting for 4–72 h (Ferrari et al., 2022). Migraine is listed by The Global Burden of Disease Study as the third most disabling disease worldwide (Vos et al., 2012). Most patients have episodic migraine, although some patients develop CM (the presence of  $\geq 15$  headache days per month). The 1- year prevalence of migraine is 8–15% worldwide, but is highly dependent on age, sex, and migraine subtype (Ferrari et al., 2015). Migraine is 40–60% determined by genetic factors and for the remainder by non- genetic risk- modulating and trigger factors. Although a progressive increase of the attack frequency can occur spontaneously, it is often aggravated and/or induced by overuse of acute headache medications and/or caffeine. Risk factors for migraine progression toward CM include high headache frequency, high headache-related disability, obesity, allodynia, anxiety, and depression (Ferrari et al., 2022). Comorbid migraine and anxiety/depression are common in the general population, but the mechanism(s) supporting the comorbidity are still unknown. Overall, there seems to be a bidirectional relationship between migraine and depression, and a shared pathophysiological mechanism has been recently outlined (Karsan & Goadsby, 2021). Indeed, in cohort studies, the risk of incident migraine in persons with existing major depression was threefold higher than in persons without depression, and incident major depression in persons with pre- existing migraine was more than fivefold higher than in persons without migraine history (Modgill et al., 2011). Comorbid anxiety/depression increases the risk of migraine chronification (Guidetti et al., 1998; Tietjen et al., 2007). However, there is no evidence that treating depression or anxiety mitigates migraine (Ferrari et al., 2022). Other psychological factors have been linked to migraine over time, as the case of alexithymia (Galli et al., 2017, Bottioli et al., 2018), traumatic events (Bottioli et al., 2019; Stensland et al., 2013), early episodes of maltreatment (Tietjen et al., 2016), personality characteristics (Bottioli et al., 2016; 2021; Galli et al., 2019).

#### FIBROMYALGIA (FM)

FM is a chronic syndrome characterized by widespread musculoskeletal pain associated with fatigue, nonrestorative sleep, and cognitive deficits (Wolfe et al., 2016) with high incidence among women (Branco

et al., 2010). The prevalence of CP comorbidities among FM patients was also high ranging from 39% to 76% (with headache and irritable bowel syndrome that were the most prevalent). Although a central sensitization phenomenon seems to play a central role in FM (Arnold et al., 2016), the etiopathology of FM remains unknown (Thieme et al., 2017). For these reasons, researchers have proposed a biopsychosocial model of interacting variables that can activate and exacerbate FM symptoms (Sommer et al., 2012). FM patients experience excessive levels of psychological distress: 20–80% experience anxiety and 13–64% experience depression (Galvez-Sánchez et al., 2019). A recent systematic review on comorbidities in FM (Kleykamp et al., 2021) found that the most prevalent comorbidity across all studies reviewed was depression/major depressive disorder with over half of the patients included having this diagnosis in their lifetime. Another interesting personality construct involved in FM is 'distressed' personality (van Middendorp et al., 2016). Moreover, nearly one-third of FM patients had current or lifetime bipolar disorder, panic disorder, or post-traumatic stress disorder. Specifically, among environmental factors, stressful life events have been considered (Nakamura et al., 2014). Trauma and major life stress are unlikely to cause FM per se. In genetically susceptible persons, it is likely that early trauma and prolonged stress in adulthood will influence brain modulatory circuitry of both pain and emotions (Crofford, 2007; Schweinhardt et al., 2008) that could explain the increased pain responses and symptoms of patients with FM. Traumatic events have been shown to influence pain severity as well (Bote et al., 2013). Several theoretical models have suggested that some personality characteristics lead to a worse response to stressors and adjustment to diseases in people with CP, such as FM (Naylor et al., 2017; Galvez-Sánchez et al., 2019). A minority of studies have focused on the detection of personality disorders associated with FM (Attademo & Bernardini, 2018). In general, previous studies found a high prevalence of avoidance (41.4%), obsessive-compulsive (33.1%) and borderline personality disorder (5.2-27.4%) in FM (Thieme et al., 2004; Uguz et al., 2010; Gumà-Uriel et al., 2016). In recent years, many studies on FM have reported a high prevalence of alexithymia (15-20%) (Di Tella et al., 2017; Marchi et al., 2019; Atzeni et al., 2019).
